STATISTICAL ANALYSIS PLAN

for

Improving Therapeutic Learning in Depression: Proof of Concept
NCT02376257

Date of Document: November 15, 2013

[name] et al. DCS, Modafinil, PBO: Data Analysis

Analyses for outliers, non-normal distributions, nonlinear relations, and influence statistics will be conducted; data transformations will be considered where appropriate. We will perform repeated-measures ANOVAs using mixed-effects regression models (MRMs) in SPSS 20.0 to analyze the data. The MRM approach to repeated measures ANCOVA allows inclusion of all participants regardless of missing data (which improves power and generalizability), can model the covariance matrix of the repeated measures more flexibly than ANCOVA, and is the recommended method for longitudinal data analysis (Hamer & Simpson, 2009). The ANCOVA will consist of 3 levels of the between-subjects IV (Treatment Condition) and 2 (or 3) levels of the within-subjects IV (Time). For delayed recall memory, Time will represent weeks 3 and 4, when recall for information presented at the previous session will be assessed. Three separate analyses will be performed, one for each of the 3 measures of delayed recall memory; retention of 1) cognitive therapy principles, 2) emotional narrative, and 3) WMS Story B (exploratory analyses will also examine cognitive therapy skill use, following this analytic approach). For immediate memory, Time will represent weeks 2 & 3, the time points of primary interest for the immediate memory tests (digit span, HVLT, ICAT). Scores on the baseline memory assessments (week 1) and baseline antidepressant use will be included as covariates in all analyses. Since the relation between the covariates and outcome may be different among treatment conditions (e.g., the relation between baseline memory and drug influenced memory may be lower for 250 DCS and 100 modafinil compared to placebo), interaction terms will allow these relations to vary across treatment conditions. Similarly, because the relation between the covariates and the DVs may be lower at weeks 2 and 3 (with drug ingestion) compared to week 4 (no drug ingestion), interaction terms will also allow these relations to vary across Time. Non-significant interaction terms will be dropped.

Aim 1. A significant main effect for Treatment Condition for “delayed memory” would indicate differences between conditions in delayed memory. In particular, we expect that pairwise comparisons among the 3 treatment conditions (using the Sidak correction for multiple comparisons [this correction is available in SPSS’s mixed effects routine]) will show that 250 DCS and 100 modafinil significantly enhance delayed memory compared to placebo.

Aim 2: A significant interaction between Treatment Condition and Time will indicate that differences between delayed recall in the “drug context” (week 3) vs. “no-drug context” (week 4) are different for different treatment conditions. Dummy variable coding for treatment condition, comparing modafinil to each of the 2 other treatment conditions, is expected to show significantly greater reduction of recall memory between weeks 3 and 4 for those taking modafinil compared to other conditions due to the change in drug context in week 4.

Aim 3: We hypothesize a Treatment Condition main effect for immediate memory, such that pairwise comparisons among the 3 conditions (using the Sidak correction for multiple comparisons) will show that 250 DCS and 100 modafinil will significantly enhance immediate memory compared to placebo.

Exploratory Analyses: We will examine whether baseline antidepressant use, mood (BDI-II), fatigue (FSS), attentional/executive function (COWAT, TMT-B), HVLT total score, and/or digits backward performance moderates active study drug effects relative to the placebo condition. Examination of associations between performance on immediate memory scores and delayed recall (including ICAT performance at Weeks 2-4) will also be examined in each study drug condition to help clarify the nature of in-session memory augmentation vs. retention effects across the weeks of testing. The effect of treatment condition on BDI will also be examined using the same analysis as Aim 1 (including pairwise comparisons among the groups). We expect BDI to be enhanced in 100 Modafinil, and explore whether it will also be enhanced in 250 DCS. We will also examine if improved memory mediates the changes in BDI.

Power Analysis. We used PinT 2.12 (a program to calculate effect sizes in mixed models) to calculate the smallest N necessary to detect a medium effect size ($d=.5$) with .80 power for the

specific hypothesized comparisons in Aims 1, 2, and 3. We conservatively assumed that 15 covariates (including interaction terms between covariates and both Treatment Condition and Time) will be included as additional predictors in each analysis (the power is greater if no interaction terms are necessary). We also assumed 10% attrition by week 4, although the mixed effects models include all participants regardless of missing data. Since there are multiple comparison tests, we used the conservative Bonferroni correction and set the p level at $.05/3=.0167$. **Aim 1:** A total sample size of 77 is necessary to detect a medium effect with .80 power. **Aim 2:** A sample size of 59 is necessary to detect a medium effect size for the interaction between time and individual treatment contrasts. **Aim 3:** Since the analysis in Aim 3 is identical to that in Aim1, 77 participants are required for Aim 3. Thus, a total sample size of 77 will give us at least .

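### Do three delayed-recall measures, tested without a correction across them, call for a new multiplicity rule?

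*SAP*

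**What the plan says.** The Data Analysis section of the SAP fits one mixed model per outcome: "Three separate analyses will be performed, one for each of the 3 measures of delayed recall memory", namely cognitive therapy principles, the emotional narrative and WMS Story B.

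Under Aim 1, a treatment main effect "would indicate differences between conditions in delayed memory". It is followed by "pairwise comparisons among the 3 treatment conditions (using the Sidak correction for multiple comparisons"; the SAP notes that SPSS's mixed-model routine supplies this correction, so it acts within one model. The expected result is that "250 DCS and 100 modafinil significantly enhance delayed memory compared to placebo".

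The Power Analysis has a single factor of three: "Since there are multiple comparison tests, we used the conservative Bonferroni correction and set the p level at" .05/3 = .0167.

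Aim 3 repeats the structure for digit span, HVLT and ICAT: "Since the analysis in Aim 3 is identical to that in Aim1, 77 participants are required for Aim 3". Aim 2 uses dummy coding, "comparing modafinil to each of the 2 other treatment conditions", on the same three delayed-recall outcomes.

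The protocol (Research Design and Methods) names two primary outcomes, therapy content and logical memory retention. Its section on delayed-recall assessments lists the WMS and the emotional story as separate tests, so it is not plain whether the primary set has two members or three.

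**The concern.** Aim 1 reads as one claim about delayed memory, but it is tested three times. The factor of three in the power section can cover three treatment pairs or three measures, not both, and Sidak as described uses it for the pairs. With no rule on how many measures must succeed, a win on any one could be presented as support for the Aim. A reader might then take each drug-placebo claim as protected at 5% for the Aim as a whole, when that protection stops at the single measure. Aims 2 and 3 share the structure.

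**Working it through.** **Inputs.** From the SAP: three measures, Sidak over three pairs, planning alpha .05/3, d = .5, power .80, N = 77 for Aim 1. Assumed, because the documents do not give them: two-sided tests; 1:1:1 allocation, so that the two drug-placebo statistics correlate .5 through the shared placebo arm; correlation rho between measures from 0 to .9. Error and power come from simulated normal test statistics (400,000 to 1,000,000 trials per setting).

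**The plan's own figures.** .05/3 = .0167 reproduces. The Sidak level is 1 − .95^(1/3) = .01695, so analysis and sizing agree. N = 77 cannot be rebuilt. The plain two-sample formula gives 2 × (2.394 + .842)² / .5² ≈ 84 per arm, or 252. Reaching 77 needs a contrast variance of 77/252 = .31 of the single-visit variance. Averaging two weeks and covariate adjustment could supply that, for example (1 + .5)/2 × (1 − .6) = .30, but those inputs are not reported. So 77 is neither confirmed nor shown to be wrong. The comparison below does not need it: both rules are set at the plan's stated .80 at .0167, a noncentrality of 2.394 + .842 = 3.236.

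**Error as the plan stands.** On one measure, two drug-placebo tests at .01695 give 3.2%. Three independent measures give 1 − (1 − .032)³ ≈ 9.3%; two give 1 − (1 − .032)² ≈ 6.3%. The bound with all six tests independent is 1 − .95² = 9.75%. When no drug works:

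| Chance of at least one false drug-placebo finding | rho 0 | rho .5 | rho .9 |
|---|---|---|---|
| Three measures, either direction | 9.3% | 8.4% | 5.6% |
| Three measures, false enhancement only | 4.7% | 4.2% | 2.8% |

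With two measures (either direction) the figure runs from 6.3% at rho 0 to 4.6% at rho .9. Requiring a significant main effect first, as the wording of Aim 1 suggests, changes the three-measure range only to 8.9%–5.4%. Aim 3 has the same figures. Aim 2's two modafinil contrasts give 9.1%, 8.2% and 5.6% if each is tested at .0167.

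**What a rule across measures would do.** The natural candidate is Hommel's procedure over the three measures at .025 per drug, raised to .05 for the other drug after a full success. Its drug-placebo error when no drug works is 4.7%, about 4.5% and 3.4% at rho 0, .5 and .9. Power per drug-placebo test:

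| True effects | Plan | Hommel rule |
|---|---|---|
| Both drugs, all three measures | .80 | .84–.85 |
| One drug, all three measures | .80 | .80–.82 |
| Drug works on two measures | .80 | .76 |
| Drug works on one measure | .80 | .73 |

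The last row can be checked by hand. A lone effect must pass about .025/3 = .0083 (z = 2.638), so power is Φ(3.236 − 2.638) = Φ(.598) = .725. At the Sidak level (z = 2.388) it is Φ(.848) = .802.

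If any one success counts as support, the relevant power is the chance of at least one success per drug. At rho .5:

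| True effects | Plan | Hommel rule |
|---|---|---|
| That drug only, all three measures | .95 | .92 |
| Both drugs, effects of 100%, 75% and 50% of plan | .85 | .80 |
| Drug works on one measure | .81 | .73 |

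**The third pair.** Suppose DCS versus modafinil stays at .0170, read on a measure only after a drug has beaten placebo there. Error over all three pairs is then not held at 5%. If both drugs work equally on two measures it is 7.1% (rho 0) and 6.5% (rho .5), against 7.6% and 7.2% now. If one drug works on three measures and the other on two, it rises from 5.0% to 6.6% (rho 0) and from 4.8% to 6.4% (rho .5).

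**The case for a change.** The strongest case for a change is consistency. The sponsor chose to correct for multiple comparisons and sized the trial for it; correcting over pairs while leaving the measures free stops halfway. The excess is real: with three measures, every correlation from 0 to .9 gives more than 5%. False enhancement of 4.7% at correlation 0 is nearly twice the 2.5% that a two-sided 5% test allows in one direction. A Hommel rule needs only new SAP wording, and under the sponsor's own hypothesis that both drugs work it gains power per test.

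The arithmetic in that case stands. The inference to a required change does not. The power gain depends on both drugs having full, equal effects on all three measures, which the documents do not claim for therapy content, an emotional story and a neutral one. With unequal or partial effects the rule loses power, and it does not hold 5% once DCS versus modafinil is included. Extending it to Aims 2 and 3 as secondary families would also impose a ranking that the SAP does not make, since its power section addresses all three Aims. It remains true that stating the primary set and the meaning of success would make the plan clearer.

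**Conclusion.** The observation is correct but no change follows. Read as success on any one of three measures, Aim 1 carries a 9.3% to 5.6% chance of some false drug-placebo finding; with the protocol's two primary outcomes it is 6.3% to 4.6%. These figures assume two-sided tests, equal allocation, no true effect and outcome correlations of 0 to .9, none of which the documents settle. Each measure taken alone is held to 3.2% for its drug-placebo pair of tests, inside the 5% that Sidak promises, and the SAP claims no control beyond that.

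A stricter rule would exchange a few points of type I error for up to 7 or 8 points of power where a drug helps only some kinds of memory. In a proof-of-concept study, experienced statisticians could choose either side. Whether the emotional narrative is primary, and how many measures must succeed, is missing detail rather than a faulty method. Reporting all three prespecified results, with the Sidak adjustment described as applying within a measure, lets a reader judge the Aim correctly.

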### Design Considerations

Why Investigate Baseline Cognitive Impairment? Cognitive (including verbal memory) impairments have been documented in unipolar depression (e.g., Castaneda et al., 2008; [name] et al., 1994), with poorer neuropsychological functioning predicting poorer antidepressant (e.g., Dunkin et al., 2000; Kampf-Sherf et al., 2004; *Withall et al., 2009* as well as CBT response (Dobkin et al., 2012; see also Caudle et al., 2007). Because there is a potential for stronger cognitive enhancement effects among individuals with greater cognitive dysfunction (e.g., such effects have been reported for modafinil administration in healthy participants; Finke et al., 2010), baseline cognitive functioning will be examined as a potential moderator of augmentation effects in the present study. In addition, these baseline measures will serve as covariates, providing potentially greater power for detection of drug effects.

Why Utilize 2 Drug Administration Visits and A Follow-Up Visit? As noted in the “Context...” section above, this study examines the effects of study drugs on the day of administration and during subsequent weeks. By keeping the final visit drug-free, we will be able to examine retention of memory when individuals are drug-free (across drug-cue contexts). Use of two isolated administrations of study drug matches the original and subsequent applications of DCS for specific phobia (Ressler et al., 2004; Smits et al., in press).

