### Randomization and Study Drugs

Participants will be block randomized (by sex and SSRI use) to one of the **3** drug conditions. Study drugs will be provided in identical capsules. Patients will receive one capsule of their randomized drug on Study Visit 2 and one capsule on Study Visit 3. At these visits, study capsule administration will be observed and precede cognitive testing by 90 minutes. Similar timing has been the standard in our studies of DCS augmentation; and is appropriate to the absorption and half-life of modafinil (Darwish et al., 2010).

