### **Procedures**

- **Visit 1: Screening and Baseline Assessment.** Following phone screening, patients will be scheduled for an evaluation session where informed consent will be obtained. The psychiatric evaluation begins with the Structured Clinical Interview (SCID) to evaluate the presence of psychiatric inclusion and exclusion criteria. Patients will also complete a medical history form and interview with the study physician. If inclusion criteria are met, baseline questionnaires and cognitive assessment :administration of the WMS--Logical Memory (Story A), Digit Span, Hopkins Verbal Learning Test, Trails A and B, and the Controlled Oral Word Association Test (see below). Participants will then be scheduled for 3 subsequent weekly assessment sessions, with randomization in a double-blind fashion using a random number list to receive one of the 4 study conditions. Randomizations will be blocked by sex and SSRI use and will occur at week 2.
- **Visit 2: Study Drug Administration and Assessment.** At this visit, patients will first complete the BDI and FSS followed by administration of the randomized study capsule 90 minutes before initiation of cognitive testing procedures. During the waiting period, magazines and television videotapes will be provided. Drug adverse effects will be queried at the end of this waiting period for symptoms over the last hour as well as emergent symptoms occurring after the last study session. For cognitive testing, participants will listen to the WMS Logical Memory story B, followed by immediate recall. Similar procedures will then be followed for the Emotional Logical Memory Task. Participants will then complete unique versions (to the study week) of Digit Span-Backwards, HVLT, and ICAT. Finally, participants will complete a 45min portion of computerized CBT providing an overview of cognitive therapy and experience with cognitive errors.
- **Visit 3: Study Drug Administration and Assessment.** Study drug administration and assessment procedures match Visit 2, but with the addition of one-week delayed recall of both the WMS Logical Memory story B and the Emotional Logical Memory Task. CTAS and SoCT are specific to the previous week's content, and a novel 45min portion of computerized CBT (cognitive schema work) is presented.

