- **Visit 4: Final Assessment.** No study drug is administered. Participants will first complete the BDI and FSS followed by one-week delayed recall of the WMS Logical Memory story B, followed by one week delayed recall of the Emotional Logical Memory Task. Then, in turn, each story will be retold, and followed by an immediate recall session. Participants will then complete the Cognitive Therapy Awareness Scale (for the previous weeks CBT content) **and SoCT** followed by a unique Digit Span-Backwards, HVLT, and ICAT.

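### Sex is a randomisation blocking factor but is in no model, and the exploratory BDI model names no baseline BDI: small, free gains in precision are left unused

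*SAP*

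**What the plan says.** **Randomisation.** The protocol gives the blocking factors twice. Under Randomization and Study Drugs: "Participants will be block randomized (by sex and SSRI use) to one of the" three conditions. Under Procedures, Visit 1: "Randomizations will be blocked by sex and SSRI use and will occur at week 2".

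**Covariates.** The SAP's Data Analysis text fixes the adjustment set: "Scores on the baseline memory assessments (week 1) and baseline antidepressant use will be included as covariates in all analyses". Antidepressant use covers the SSRI factor; sex is not named. The protocol's section on covariates and weekly memory tasks adds Digit Span, COWAT and Trails B as covariates, again without sex. The exploratory moderator list also omits it: "We will examine whether baseline antidepressant use, mood (BDI-II), fatigue (FSS), attentional/executive function (COWAT, TMT-B), HVLT total score", plus digits backward. The Power Analysis allows for 15 covariates but does not itemise them.

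**BDI.** Under Exploratory Analyses: "The effect of treatment condition on BDI will also be examined using the same analysis as Aim 1". No baseline BDI is named for that model; BDI-II appears as a predictor only in the moderator list. At Visit 2, before any drug, "patients will first complete the BDI and FSS followed by administration of the randomized study capsule". Visit 3 follows the Visit 2 procedures, and at Visit 4 "Participants will first complete the BDI and FSS followed by one-week delayed recall".

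**Stated reason for covariates.** Protocol, Design Considerations, on the baseline cognitive measures: "these baseline measures will serve as covariates, providing potentially greater power for detection of drug effects".

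**The concern.** There are two separate points.

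1. **Sex.** When allocation is balanced within sex, the true variance of a between-arm difference contains almost no contribution from sex. A model without sex still counts that contribution as residual noise. If sex predicts the outcome beyond the other covariates, the reported standard error exceeds the true one, the test runs below its nominal level, and power is lost. One blocking factor is modelled and the other is not, and no reason is given.

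2. **Baseline BDI.** Week 1 memory scores are natural covariates for memory outcomes. Carried over unchanged to BDI, they leave out what is usually the strongest predictor of a later BDI, namely an earlier one. Here the standard error would be valid, but larger than it need be.

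At stake is precision, not validity. The protocol's own argument for covariates applies equally to these two variables, and both are already collected.

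**Working it through.** **Inputs from the documents.** Three arms; N = 77; d = .5; power .80; per-comparison level .05/3 = .0167 (SAP, Power Analysis); Sidak-corrected pairwise tests (SAP, Aims 1 and 3).

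**The plan's own figures.** .05/3 = .0167 reproduces. N = 77 does not follow from the printed inputs alone: an unadjusted two-sided comparison at .0167 needs 84 per arm, 252 in total, or 252/.9 = 280 with 10% attrition. The variance and correlation inputs to the power program are not given, so 77 is neither confirmed nor refuted. Nothing below depends on it.

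**Sex: formulas.** Let R² be the share of the residual variance of a person's two-visit mean that sex explains after the other covariates. The documents give no value, so a range is assumed. With sex balanced across arms:

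- reported SE / true SE: k = 1/√(1 − R²)
- actual level of a two-sided test with critical value z: 2[1 − Φ(z·k)]
- Sidak level per pair: 1 − .95^(1/3) = .0170
- power without sex, where it is .80 with sex at .0167 (z = 2.39): Φ(2.39 + .842 − 2.39·k)
- sex difference implied by R² with equal numbers of each sex, in residual SDs of the two-visit mean: 2√R²

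| R² (assumed) | Implied sex difference | k | Level, nominal .05 | Level, nominal .0170 | Power without sex |
|---|---|---|---|---|---|
| .01 | 0.20 | 1.005 | .0489 | .0164 | .797 |
| .03 | 0.35 | 1.015 | .0466 | .0153 | .790 |
| .06 | 0.49 | 1.031 | .0432 | .0138 | .778 |
| .10 | 0.63 | 1.054 | .0388 | .0118 | .762 |

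**Sex: simulation with exact balance.** 40,000 runs, 26 per arm, sex balanced within arm, two visits correlated .5, R² = .10. For the two-visit mean (Aims 1 and 3), the reported SE without sex is .241 against a true SD of .227, and a nominal 5% test runs at .038. With sex, the reported SE is .228 and the level .050. For the visit difference (Aim 2), the SE is .277 with or without sex, against a true SD of .278, because a constant sex effect cancels.

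**Sex: simulation with realistic blocking.** N = 77, permuted blocks of 6 within sex × SSRI strata, level .0167, drug effect 0.5, 6,000 runs per setting; 60% women and 40% SSRI users assumed. The sex effect here is in SDs of the simulated outcome, a different scale from the table above.

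| Sex effect beyond covariates | Mean SE without → with sex | Ratio | Power without → with sex | Null rejection without / with sex |
|---|---|---|---|---|
| 0 | .1985 → .1986 | 1.00 | 53% → 53% | .0167 / .0167 |
| 0.3 SD | .2025 → .1984 | 1.02 | 51% → 53% | .0152 / .0168 |
| 0.5 SD | .2099 → .1981 | 1.06 | 48% → 54% | .0142 / .0215 |
| 0.8 SD | .2276 → .1984 | 1.15 | 39% → 53% | .0070 / .0147 |

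The null rejection rates carry a Monte Carlo error of about √(.0167 × .9833/6000) = .0017, so they show direction better than exact size. Bias was negligible throughout.

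**BDI.** Assume any two BDI visits correlate r, with weeks 3 and 4 as outcomes. The two-visit mean has variance (1 + r)/2 and covariance r with the pre-dose score. The share explained is r²/[(1 + r)/2] = 2r²/(1 + r), and the width ratio without the baseline is 1/√(1 − share).

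| r (assumed) | Share explained | Width ratio |
|---|---|---|
| .3 | .138 | 1.077 |
| .5 | .333 | 1.225 |
| .7 | .576 | 1.537 |

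If the week 3 to week 4 correlation is instead set at .6 to .8, omitting the baseline makes the SE 18–21% larger at a baseline correlation of .5, and 48–61% larger at .7.

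**The case against.** **The sex effect is assumed and may be trivial.** This stands as a limit on size. After week 1 memory, SSRI use and perhaps Digit Span, COWAT and Trails B, sex can add only what is left. The 10% row implies a sex difference of about 0.63 residual SDs, which nothing in the documents supports. At 1% to 3% the power loss is .003 to .010. It does not remove the asymmetry between the two blocking factors, and with no sex effect the simulated results with and without sex are almost identical.

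**The BDI sentence may be a template.** Reusing the Aim 1 analysis could mean the same model form with the outcome's own baseline in the role of week 1 memory. The SAP's mediation sentence refers to change in BDI, which presupposes some baseline. This is a fair reading, and under it no precision is lost. But the SAP does not say so, and the mediation sentence does not define the covariates of the BDI comparison. The BDI time points are also open: the SAP allows two or three levels of Time, BDI is taken at Visits 2, 3 and 4, and Visit 1 has unnamed baseline questionnaires.

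**Aim 2 is not exactly invariant.** With the assumed 10% attrition, a mixed model also uses people with one visit, so the cancellation is not perfect. The effect should be tiny.

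**Conclusion.** Both points hold, and both are minor.

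- **Sex:** for R² of 1% to 10%, reported standard errors in the Treatment Condition tests are 0.5% to 5.4% too large, and .80 power becomes .797 to .762. The error is conservative and there is no bias. A larger loss would need a strong sex effect that the baseline measures do not absorb. Aim 2 is essentially untouched.
- **BDI:** on the literal reading, intervals are about 8%, 22% or 54% wider at correlations of .3, .5 or .7, and less so if the memory covariates already explain some BDI variance. The analysis is exploratory and its standard error is valid.

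The figures assume equal allocation, two-sided tests, roughly normal outcomes, blocking that achieves near-balance by sex (block size is not stated), and the R² and correlation ranges shown.

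**What to change.** - State in the SAP that sex enters as a main-effect covariate in the models that test Treatment Condition (Aims 1 and 3, and BDI). Aim 2 shares the delayed-recall model, so it will carry the term with no material effect.
- State that the BDI model has week 3 and week 4 BDI as outcomes and adds the pre-dose Visit 2 BDI as a covariate, alongside the existing covariates rather than in place of them. If the outcome's own baseline was always intended, this sentence simply records it.

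**Cost.** One or two sentences, no new data, and one degree of freedom per added covariate. Under the SAP's interaction rule, each new covariate could start with up to four (1 main + 2 with Treatment Condition + 1 with Time) before non-significant interactions are dropped. Specifying main effect only for sex keeps it at one.

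### Dropping non-significant Treatment-by-covariate terms, with no stated covariate value for the Treatment test, inflates the Aim 1 and Aim 3 omnibus test if baseline scores are uncentred

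*SAP*

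**What the plan says.** The SAP's Data Analysis section sets up a mixed model with three arms and two or three time levels. On covariates it says: "Scores on the baseline memory assessments (week 1) and baseline antidepressant use will be included as covariates in all analyses". It then adds heterogeneous slopes: "interaction terms will allow these relations to vary across treatment conditions". The reason given is that "the relation between baseline memory and drug influenced memory may be lower for 250 DCS and 100 modafinil compared to placebo". Covariate slopes may also vary over Time. The rule for simplifying the model is one sentence: "Non-significant interaction terms will be dropped". No significance level or order of removal is given.

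Under Aim 1, a significant Treatment main effect on delayed memory "would indicate differences between conditions in delayed memory"; Sidak pairwise comparisons follow. Aim 3 has the same structure: "We hypothesize a Treatment Condition main effect for immediate memory".

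The Power Analysis budgets for the interactions: "We conservatively assumed that 15 covariates (including interaction terms between covariates and both Treatment Condition and Time". It sets .05/3 = .0167 as the level for the sample size. The level for the omnibus test itself is not stated. Neither document mentions centring, or the covariate value at which the omnibus test or the Sidak pairs are evaluated.

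**The concern.** Once a Treatment-by-covariate product is in the model, the Treatment main effect is the arm difference where that covariate equals zero. For a raw HVLT score (12 nouns, three trials, per the Protocol's section on covariates and weekly memory tasks), zero means recalling no noun on any trial. If every such product has been dropped, the same line of output is the average arm difference. A significance test on the trial's own data therefore decides which hypothesis is tested.

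The two outcomes are not neutral under the null. A slope difference that survives by chance brings with it a spurious arm difference at zero when zero lies far from the observed scores. The test named for Aims 1 and 3 can then exceed its level. Separately, if slopes really are flatter on the drugs, as the SAP anticipates, a test at zero does not address the average drug effect at all.

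**Working it through.** **Plan's own figures.** The documents give no error rate for this procedure, so there is none to reproduce. The level .05/3 = .0167 is correct arithmetic. N = 77 cannot be rebuilt without the variance components used in the power program, but it does not bear on this point and is taken as given.

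**Inputs from the documents.** 77 participants (simulated 26/26/25), three arms, two time points, 10% attrition (8 of 77 missing the second time point), d = .5, 15 covariate terms.

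**Inputs assumed.** Backward dropping at .05; omnibus alpha .05; covariate R-squared .3; correlation between scores .3; within-person residual correlation .5; antidepressant use about 40%; score mean/SD from 0 to 5.

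**Step 1: what is tested.** For arms j and j′, the difference at covariate values x is D(x) = (τ_j − τ_j′) + Σ_k (δ_jk − δ_j′k) x_k. The main effect is D(0). The average effect is D at the covariate means. They coincide only if every δ difference is zero (term dropped) or the covariates are centred.

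**Step 2: why selection matters.** Take one covariate with mean/SD = m. The estimated D at the mean is nearly independent of the estimated slope difference, so the correlation of D(0) with the slope difference has size m/√(1+m²). For m = 0, 1, 2, 3, 5 this is 0, .71, .89, .95, .98. Keeping the term only when the slope difference is large therefore tends to keep it when D(0) is large.

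**Step 3: how many covariates.** Each covariate uses 1 main + 2 Treatment + 1 Time = 4 terms, and 15/4 = 3.75, so three fit the budget. The Protocol's Visit 1 lists three memory tests; one score from each plus antidepressant use makes 4 × 4 = 16 terms, one over. The headline therefore uses two or three covariates (one or two scores plus antidepressant use).

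**Step 4: null simulation.** Random-intercept REML, 5000 trials per setting, simulation SE about .002 to .005. Omnibus rejection at raw zero after selection:

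| Covariates | m=0 | m=1 | m=2 | m=3 | m=5 |
|---|---|---|---|---|---|
| 2 | 5.6% | 7.1% | 8.4% | 8.9% | 9.6% |
| 3 | 5.3% | 8.1% | 10.7% | 11.8% | 12.7% |
| 4 (one over budget) | 6.9% | 10.5% | 13.5% | 15.1% | 16.5% |

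Antidepressant use is centred in the first two rows and coded 0/1 in the third, so the third is not strictly like for like. With 0/1 coding the three-covariate row is 6.2/8.5/10.7/11.9/12.8%. A Treatment-by-covariate term survives by chance in 10.3%, 15.0% and 19.0% of trials with 2, 3 and 4 covariates.

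**Step 5: one element at a time.** Selection, tested at covariate means: 5.7% (2 covariates) and 5.3% (3). All interactions kept, tested at zero: 4.9-5.2% (2) and 4.8-5.3% (3). Material inflation needs both selection and raw zero.

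**Step 6: Sidak pairs after selection.** Any of three significant: 4.7-5.1% at means; 7.7-11.4% at zero (2-3 covariates, m = 2 to 5). Requiring the omnibus test at zero plus at least one pair at means: 4.2-4.8%.

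**Step 7: at .0167.** Omnibus at zero after selection is 3.1-5.4% (2-3 covariates, m = 2 to 5), against 1.8-1.9% at means. The first range is about 1.9 to 3.2 times the level.

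**Step 8: repeat simulations.** A separate mixed-model simulation (R-squared .4, antidepressant use 0/1, 1200 trials per setting) gave 8.0-13.2% at m = 2 and 5, and 5.7-8.1% at m = 0 and 1. Least squares on subject means with complete data gave 8.9-9.8% (2 covariates) and 10.9-14.0% (3) at m = 2 to 5, against 4.5-5.7% at means. The highest value in any two- or three-covariate setting was 15.5%, with three continuous uncorrelated scores.

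**Step 9: mismatch of question (not type I error).** If drug slopes were half the placebo slope (size assumed) with no average drug effect, the selected model rejects in 22.0% at zero (m = 3) and 5.3% at means.

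**The case against.** The strongest reply is that the SAP never says scores will be entered raw. Significance-based dropping, the only element it states, does little harm by itself, so this is an unstated detail rather than a stated error. That stands as far as it goes: the inflation is conditional on uncentred scores.

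Second, the drug-versus-placebo hypotheses are framed as Sidak comparisons, and these hold their level at covariate means, as does requiring both the omnibus test and a pair. This also stands and limits the harm. But the Aim 1 text treats a significant main effect as evidence in its own right, does not require a pair to confirm it, and does not say where the pairs are evaluated.

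Third, mean/SD, covariate count, R-squared, dropping level and omnibus alpha are all assumed. They are, which is why ranges are given. At the only level the SAP states, .0167, absolute rates for two or three covariates do not go far above 5%, though they still exceed that level. Runs with more than three covariates strain the 15-term budget and are kept out of the headline.

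Finally, this is a proof-of-concept study. That lowers the stakes but not the case for a free clarification.

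**Conclusion.** The concern holds, conditionally. If baseline scores are uncentred and Treatment is read from the main-effect line, the omnibus test for Aims 1 and 3 runs at about 8-13% instead of 5% with two or three covariates at mean/SD 2-5, and at 5-8% at mean/SD 0-1. These figures rest on the assumed dropping level, omnibus alpha, R-squared, correlations and mean/SD; repeat simulations under different assumptions agree closely. Pairwise conclusions taken at covariate means are not affected; taken at zero, they are. The evaluation point should be settled before analysis. It is not a fatal flaw, and confidence is medium because the documents do not give the inputs that set the size.

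**What to change.** Add one sentence to the SAP: all baseline covariates, including antidepressant use, are grand-mean-centred, and both the omnibus Treatment test and the Sidak comparisons for Aims 1 and 3 are evaluated at covariate means. This keeps the heterogeneous slopes and the interest in baseline cognition as a moderator set out in the Protocol's Design Considerations.

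Also state the omnibus alpha, since .0167 appears only in the Power Analysis. Optionally, name in advance which Treatment-by-covariate terms enter the primary model.

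Keeping every interaction while still testing at zero is not a substitute. It restores the level, but with both drugs at d = .5 and three covariates, power is 13.1%, 8.5% and 6.0% at mean/SD 2, 3 and 5, against 66.6% at covariate means with the same terms kept (3000 trials per setting).

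The cost is SAP wording only: no new data, no extra participants, and no loss of planned terms.
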